#### **11.4.4 Sensitivity analyses**

As a sensitivity analysis, the change from baseline in free T at Day 15 will be analyzed in an analysis of covariance model of the same form as the one specified for the primary analysis, except no logarithmic transformation will be applied. The least-squares mean change from baseline will be estimated from the model for LIK066 and placebo, along with the treatment difference and the associated p-value and two-sided 90% confidence interval.

### **11.5 Analysis of secondary variable(s)**

The secondary variables will be the gonadotropins (LH and FSH), the sex steroids (total testosterone, estradiol, progesterone, DHEAS, DHEA, androstenedione), SHBG, and free androgen index. For LH, FSH, and total testosterone, the average of the three morning fasting concentrations will be additional secondary variables.

#### **11.5.1 Efficacy / Pharmacodynamics**

Each of the secondary variables will be listed by treatment group, subject, and visit/time and summarized by treatment and visit/time. The change from baseline and % change from baseline will also be listed and summarized.

## **11.5.2 Safety**

### **Vital signs**

All vital signs data will be listed by treatment group, subject, and visit/time and if ranges are available abnormalities (and relevant orthostatic changes) will be flagged. Summary statistics will be provided by treatment and visit/time.

### **ECG evaluations**

All ECG data will be listed by treatment group, subject and visit/time, abnormalities will be flagged. Summary statistics will be provided by treatment and visit/time.

### **Clinical laboratory evaluations**

All laboratory data will be listed by treatment group, subject, and visit/time and if normal ranges are available abnormalities will be flagged. Summary statistics will be provided by treatment and visit/time.

### **Adverse events**

All information obtained on adverse events will be displayed by treatment group and subject.

The number and percentage of subjects with adverse events will be tabulated by body system and preferred term with a breakdown by treatment. A subject with multiple adverse events within a body system is only counted once towards the total of this body system.

### **11.5.5 Other assessments**

Not Applicable.

Corporate Confidential Information

## 11.7 Sample size calculation

The sample size for this study has been based on a relevant interventional study in a similar population of adults with PCOS ([George et al 2016](#)). The mean and standard deviation of free T by LC-MS/MS in this study, as a pooled estimate across all treatment arms at baseline, is 79 pmol/L and 40 pmol/L, respectively. The study reported a decrease in free T of 19% after 7 days of treatment with AZD4901, a neuropeptide Y receptor antagonist.

The sample size calculation assumes similar baseline characteristics of free T, a 2% reduction in free T in the placebo arm, and a correlation between baseline and Day 14 free T of 0.5. The assumption also is that the true treatment effect of LIK066 is 35% over placebo. We choose to assume a correlation between baseline and Day 15 of 0.5 because, based on results of free T in a published study of metformin in women with PCOS ([Kurzthaler et al 2014](#)), we believe it to be smaller than the true correlation, and hence it is likely that the power for achieving the primary study criteria is conservative.

Based on these assumptions, a sample size of 24 subjects in a 1:1 treatment allocation (12 on LIK066; 12 on placebo) will provide 80% probability of achieving the dual criteria specified in the previous section. The probability of a type I error (achieving the criteria when in fact there is no true treatment effect on free T) is 5%. These results are based on 10,000 simulations of the primary analysis.

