#### **11.4.2 Statistical model, hypothesis, and method of analysis**

The primary analysis will assess the treatment effect of LIK066 on free T at Day 15. The ratio of Day 15 to baseline free T will be analyzed in an analysis of covariance model with treatment as a categorical factor and baseline free T as a covariate. Additional baseline characteristics that may be predictive of free T may be added to the model as covariates. The logarithm of the ratio and of baseline free T will be applied prior to the analysis.

The geometric mean of the ratio to baseline for free T will be estimated from the model for LIK066 and placebo, along with the treatment ratio and the associated p-value and two-sided 90% confidence interval (CI). From these quantities, the following criteria will be assessed:

1. the upper confidence limit of the 90% CI is less than 1, and
2. the estimated treatment ratio is less than 0.75.

The first criterion addresses with high certainty whether the effect of LIK066 on free T reduction is superior to placebo. The second criterion addresses whether the observed treatment effect of LIK066 on free T reduction is at least 25%. An effect size of 20-25% on hyperandrogenism is considered to be clinically meaningful in PCOS as it correlates with improved ovulation and fertility ([Harborne et al 2003](#)).

Subjects who are deemed to have hormonal evidence of ovulation during the study may be excluded from the primary analysis.

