#### **6.1.3 Statistical model, assumptions and hypotheses**

The primary analysis will assess the treatment effect of LIK066 on free testosterone (T) at Day 15.

The ratio of Day 15 to baseline free T will be analyzed in an analysis of covariance model, with treatment as a categorical factor, baseline body weight and baseline free T as a covariate. Additional baseline characteristics that may be predictive of free T may be added to the model as covariates. The logarithm of the ratio and of baseline free T will be applied prior to the analysis.

The geometric mean of the ratio to baseline for free T will be estimated from the model for LIK066 and placebo, along with the treatment ratio and the associated p-value and two-sided 90% confidence interval (CI). From these quantities, the following criteria will be assessed:

1. the upper confidence limit of the 90% CI is less than 1, and
2. the estimated treatment ratio is less than 0.75.

The first criterion addresses with high certainty whether the effect of LIK066 on free T reduction is superior to placebo. The second criterion addresses whether the observed treatment effect of LIK066 on free T reduction is at least 25%. An effect size of 20-25% on hyperandrogenism is considered to be clinically meaningful in PCOS as it correlates with improved ovulation and fertility (Harborne et al 2003).

Subjects who are deemed to have hormonal evidence of ovulation during the study may be excluded from the primary analysis.

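### The stated 80% power and 5% type I error do not go together: a 35% effect on the ratio scale gives about 76% (74 to 75% with an uninformative weight covariate), and the dual rule's type I error is about 4%

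*Protocol*

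**What the plan says.** Protocol 11.7 takes baseline free testosterone from a published study in PCOS, where the mean and SD "is 79 pmol/L and 40 pmol/L, respectively". It adds "a 2% reduction in free T in the placebo arm", "a correlation between baseline and Day 14 free T of 0.5", and the assumption that "the true treatment effect of LIK066 is 35% over placebo". From 10,000 simulations it concludes that 12 per arm "will provide 80% probability of achieving the dual criteria specified in the previous section", and that the probability of meeting the criteria when there is no true effect is 5%.

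The criteria are in Protocol 11.4.2. The first is that "the upper confidence limit of the 90% CI is less than 1, and" the second is that the estimated treatment ratio is below 0.75. Both apply to an analysis of covariance of the log ratio of Day 15 to baseline, with treatment and log baseline in the model. SAP 6.1.3 keeps the criteria but fits the model "with treatment as a categorical factor, baseline body weight and baseline free T as a covariate". The public SAP text, which is partly redacted, shows no updated power figure.

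**The concern.** The 80% in Protocol 11.7 is the operating characteristic offered for a study of 24 subjects. A joint probability cannot exceed the smaller of its two parts. On the direct reading of the inputs, the first criterion alone is met less than 80% of the time, so 80% for both cannot be right on that reading. The 5% has the same difficulty: the first criterion alone already has a one-sided level of 5%, and the second removes some of those trials.

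What is at stake is how a negative result is read. On the direct reading, a true 35% effect would be missed in about 23 to 26% of trials rather than 20%. That is before any subject is excluded for ovulation or an unevaluable Day 15 profile, although the protocol allows replacements and additional subjects.

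**Working it through.** **Inputs.** From Protocol 11.7: mean 79, SD 40, correlation 0.5, 2% placebo fall, 35% effect, 12 per arm. From 11.4.2: the model and the two criteria. Not stated: the distribution, the Day 15 SD, the scale of the correlation, and whether 35% is a ratio or a difference in percentage points. Free testosterone is taken as lognormal throughout; the other unstated items are varied below.

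**Direct reading by hand.**
- Effect: 11.4.2 treats a ratio of 0.75 as a 25% effect, so 35% is 0.65, and ln 0.65 = −0.4308. The 2% placebo fall cancels from the ratio.
- Log SD = √ln(1 + (40/79)²) = 0.478.
- Residual SD = 0.4777 × √(1 − 0.5²) = 0.4137.
- Standard error = 0.4137 × √(2/12) × √1.05 = 0.173, where 1.05 allows for chance baseline imbalance.
- Criterion 1, with t(0.95; 21 df) = 1.721: Φ(0.4308/0.173 − 1.721) ≈ 0.78.
- Criterion 2: Φ((0.4308 − 0.2877)/0.173) ≈ 0.796.

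At this standard error, criterion 1 needs an estimate below about exp(−1.721 × 0.173) = 0.74. That is so close to 0.75 that either criterion may be the binding one, depending on the residual SD observed. The joint probability is therefore below both.

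**Simulation** (400,000 trials per row; percentages). The last column adds a body weight covariate unrelated to outcome (20 residual df).

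| Reading of the inputs | Geometric mean ratio | Criterion 1 | Criterion 2 | Both | Both, SAP model |
|---|---|---|---|---|---|
| Ratio 0.65, constant CV, log-scale correlation | 0.650 | 77.8 | 79.7 | 75.6 | 74.0 |
| Same, raw-scale correlation (0.528 on log scale) | 0.650 | 79.1 | 80.0 | 76.5 | 75.1 |
| 37% vs 2% fall, constant CV, log-scale correlation | 0.643 | 79.6 | 81.3 | 77.5 | 75.9 |
| Same, raw-scale correlation | 0.643 | 80.9 | 81.8 | 78.5 | 77.0 |
| Arithmetic mean ratio 0.65, Day 15 SD 40, log-scale correlation | 0.573 | 79.2 | 89.0 | 79.0 | 77.2 |
| Same, raw-scale correlation | 0.573 | 81.1 | 89.8 | 80.9 | 79.1 |
| 37% vs 2% fall, Day 15 SD 40, log-scale correlation | 0.564 | 80.6 | 90.1 | 80.5 | 78.6 |
| Same, raw-scale correlation | 0.564 | 82.6 | 90.8 | 82.4 | 80.7 |

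Across repeated runs, the first two rows give 75.5 to 76.7% for both criteria. The Monte Carlo error of the protocol's own 10,000 runs is √(0.8 × 0.2/10,000) = 0.4 points, so a gap of 3 to 4.5 points is not simulation noise.

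**Why a fixed SD of 40 gives more.** The treated mean becomes 79 × 0.98 × 0.65 = 50.3, so its CV rises to 40/50.3 = 0.79, and its log variance is ln(1 + 0.795²) = 0.490. Placebo has mean 77.4 and log variance 0.237. The ratio of geometric means is then 0.65 × exp(−(0.490 − 0.237)/2) = 0.573. The additive version gives 0.564. These are 43 and 44% reductions on the scale tested.

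**Informative weight.** In the first row, a partial correlation of 0.2, 0.3 or 0.4 between weight and outcome gives 75.1, 76.6 or 78.6% under the SAP model.

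**Type I error.** With no true effect, criterion 1 alone is met in 5.0% of trials and both criteria in 3.8 to 4.0% under the protocol model, in every variant (up to 4.1% with an uninformative weight covariate).

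**The case against.** The strongest reply is that Protocol 11.7 leaves its inputs incomplete, and some completions do give 80%. The mean and SD are on the raw scale. If the SD stays at 40 on Day 15, the joint probability is 79 to 82%. The 2% placebo fall does nothing in a purely multiplicative model with constant CV, so listing it hints at a raw-scale or additive simulation. This stands against any claim that no reading of the inputs reaches 80%. It does not rescue the sentence as written. Those readings power the trial for a 43 to 44% reduction on the tested scale, and they still give a type I error near 4%.

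A reader might also infer that the 80% was computed for criterion 2 alone, because on the direct reading that criterion gives about 80% power and just under 5% type I error. The match is real, but 11.7 says the dual criteria were simulated, and with Day 15 SD at 40 criterion 2 alone gives 89 to 91%. The origin of the figure remains an inference.

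Nor is 74% simply the SAP figure. It assumes that weight is unrelated to the outcome, and the documents give no correlation either way.

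Finally, 11.7 says 0.5 was chosen as lower than the likely correlation. In the direct reading, 0.6 gives about 79% and 0.65 about 82%, so true power may well be near 80%. But the statement in 11.7 is conditional on 0.5, and it is that statement which does not reproduce.

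**Conclusion.** The point holds in a limited form. If 35% means a treatment ratio of 0.65, as the mapping in Protocol 11.4.2 implies, and the CV is constant with correlation 0.5, the probability of meeting both criteria is about 75.5 to 76.7% under the protocol model. It is about 74 to 75% under the SAP model with an uninformative weight covariate, and 75.1 to 78.6% if weight has a partial correlation of 0.2 to 0.4. Reading 35% as percentage points with constant CV gives 77.5 to 78.5% under the protocol model. Reaching 79 to 82% needs an unstated Day 15 SD and a larger effect on the tested scale. No variant checked returns the stated pair of 80% and 5%, because the dual rule's type I error is about 4%. That second discrepancy is on the conservative side.

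A reader might go further and conclude that the study is too small. The documents do not support that: the trial is described as non-confirmatory, the shortfall on the direct reading is about 3 to 6 points, and a higher correlation would close it. What needs correcting is the stated operating characteristics, not the number of subjects.

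**What to change.** Keep 24 subjects. Rerun the simulation for the final SAP model, with the true effect defined as a ratio of geometric means, and replace both figures in Protocol 11.7. For a ratio of 0.65, constant CV and correlation 0.5, expect a joint probability of about 74 to 77%, higher if weight is informative or the correlation exceeds 0.5, and a type I error of about 4%. The replacement should be the rerun result with its assumptions beside it, not a figure copied from this review.

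State the distribution used, the Day 15 SD in each arm, the scale of the correlation, the definition of the 35% effect and the assumed relation of body weight to outcome. Report the probability of each criterion alone beside the joint one.

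The cost is one rerun and a few sentences, with no additional subjects. The downside is a slightly less favourable stated power.

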## 11.8 Power for analysis of key secondary variables

Not Applicable.

Corporate Confidential Information

# 12 Ethical considerations

## 12.1 Regulatory and ethical compliance

This clinical study was designed and shall be implemented, executed and reported in accordance with the ICH Harmonized Tripartite Guidelines for Good Clinical Practice, with applicable local regulations (including European Directive 2001/20/EC, US Code of Federal Regulations Title 21, and Japanese Ministry of Health, Labor, and Welfare), and with the ethical principles laid down in the Declaration of Helsinki.

## **12.2 Responsibilities of the investigator and IRB/IEC**

Before initiating a trial, the investigator/institution must obtain approval/favorable opinion from the Institutional Review Board/Independent Ethics Committee (IRB/IEC) for the trial protocol, written informed consent form, consent form updates, subject recruitment procedures (e.g. advertisements) and any other written information to be provided to subjects. Prior to study start, the investigator is required to sign a protocol signature page confirming his/her agreement to conduct the study in accordance with these documents and all of the instructions and procedures found in this protocol and to give access to all relevant data and records to Novartis monitors, auditors, Novartis Quality Assurance representatives, designated agents of Novartis, IRBs/IECs, and regulatory authorities as required. If an inspection of the clinical site is requested by a regulatory authority, the investigator must inform Novartis immediately that this request has been made.

For multi-center trials, a Coordinating Investigator will be selected by Novartis by the time of Last Patient Last Visit to be a reviewer and signatory for the clinical study report.

## **12.3 Publication of study protocol and results**

The key design elements of this protocol will be posted in a publicly accessible database such as clinicaltrials.gov. In addition, upon study completion and finalization of the study report the results of this trial will be either submitted for publication and/or posted in a publicly accessible database of clinical trial results.

## **12.4 Quality Control and Quality Assurance**

Novartis maintains a robust Quality Management (QM) system that includes all activities involved in quality assurance and quality control, including the assignment of roles and responsibilities, the reporting of results, and the documentation of actions and escalation of issues identified during the review of quality metrics, incidents, audits and inspections.

Audits of investigator sites, vendors, and Novartis systems are performed or overseen by Novartis Pharma Auditing and Compliance Quality Assurance (or CRO working on behalf of Novartis), a group independent from those involved in conducting, monitoring or performing quality control of the clinical trial. The clinical audit process uses a knowledge/risk based approach.

Audits are conducted to assess GCP compliance with global and local regulatory requirements, protocols and internal SOPs, and are performed according to written Novartis processes.

## **13      Protocol adherence**

This protocol defines the study objectives, the study procedures and the data to be collected on study participants. Additional assessments required to ensure safety of subjects should be administered as deemed necessary on a case by case basis. Under no circumstances is an investigator allowed to collect additional data or conduct any additional procedures for any research related purpose involving any investigational drugs under the protocol.

Investigators ascertain they will apply due diligence to avoid protocol deviations. If an investigator feels a protocol deviation would improve the conduct of the study this must be considered a protocol amendment, and unless such an amendment is agreed upon by Novartis and approved by the IRB/IEC and health authorities, where required, it cannot be implemented.

### **13.1    Protocol Amendments**

Any change to the protocol can only be made in a written protocol amendment that must be approved by Novartis, Health Authorities where required, and the IRB/IEC prior to implementation.

Amendments that are intended to eliminate an apparent immediate hazard to subjects may be implemented immediately, provided the Health Authorities are subsequently notified by protocol amendment and the reviewing IRB/IEC is notified.

Notwithstanding the need for approval of formal protocol amendments, the investigator is expected to take any immediate action required for the safety of any subject included in this study, even if this action represents a deviation from the protocol. In such cases, the reporting requirements identified in [Section 9](#) (Safety Monitoring) must be followed and the Study Lead informed.

## 15 Appendix 1: Liver Event Definitions and Follow-up Requirements

**Table 15-1 Liver Event Definitions**

Definitions	Thresholds
Potential Hy's law cases	ALT or AST $> 3 \times$ ULN and TBL $> 2 \times$ ULN without initial increase in ALP to $> 2 \times$ ULN
ALT or AST elevation with coagulopathy	ALT or AST $> 3 \times$ ULN and INR $> 1.5$ (in the absence of anticoagulation)
ALT or AST elevation accompanied by symptoms	ALT or AST $> 3 \times$ ULN accompanied by (general) malaise, fatigue, abdominal pain, nausea, or vomiting, or rash, or eosinophilia
Isolated ALT or AST elevation	ALT or AST $> 8 \times$ ULN $5 \times$ ULN $<$ ALT/AST $\leq 8 \times$ ULN $3 \times$ ULN $<$ ALT/AST $\leq 5 \times$ ULN
Isolated ALP elevation	ALP $> 2 \times$ ULN (in the absence of known bone pathology)
Others	Any clinical event of jaundice (or equivalent term) Any adverse event potentially indicative of liver toxicity

**Table 15-2 Actions required for Liver Events**

Criteria	Action required
Potential Hy's Law case	Discontinue the study treatment immediately Hospitalize, if clinically appropriate Establish causality Complete CRFs per liver event guidance*
ALT or AST elevation with coagulopathy	
ALT or AST elevation accompanied by symptoms	
Isolated ALT or AST elevation $> 8 \times$ ULN	
Jaundice	
Isolated ALT or AST elevation $> 5$ to $\leq 8 \times$ ULN	If confirmed, consider interruption or discontinuation of study drug If elevation persists for more than 2 weeks, discontinue the study drug Establish causality Complete CRFs per liver event guidance*
Isolated ALT or AST elevation $> 3$ to $\leq 5 \times$ ULN (patient is asymptomatic)	Monitor liver chemistry tests two or three times weekly
Isolated ALP elevation	Repeat liver chemistry tests within 48-72 hours If elevation is confirmed, measure fractionated ALP; if $>50\%$ is of liver origin, establish hepatic causality Complete CRFs per liver event guidance*
Any AE potentially indicative of liver toxicity	Consider study treatment interruption or discontinuation Hospitalize if clinically appropriate Complete CRFs per liver event guidance*

\*Liver event guidance for CRF completion is available in the Site Operations Manual

**Table 15-3 Exclusion of underlying liver disease**

Disease	Assessment
Hepatitis A, B, C, E	IgM anti-HAV; HBSAg, IgM anti-HBc, HBV DNA; anti-HCV, HCV RNA, IgM & IgG anti-HEV, HEV RNA
CMV, HSV, EBV infection	IgM & IgG anti-CMV, IgM & IgG anti-HSV; IgM & IgG anti-EBV
Autoimmune hepatitis	ANA & ASMA titers, total IgM, IgG, IgE, IgA
Alcoholic hepatitis	Ethanol history, GGT, MCV, CD-transferrin
Nonalcoholic steatohepatitis	Ultrasound or MRI
Hypoxic/ischemic hepatopathy	Medical history: acute or chronic CHF, hypotension, hypoxia, hepatic venous occlusion. Ultrasound or MRI.
Biliary tract disease	Ultrasound or MRI, ERCP as appropriate.
Wilson disease	Caeruloplasmin
Hemochromatosis	Ferritin, transferrin
Alpha-1-antitrypsin deficiency	Alpha-1-antitrypsin

## 16 Appendix 2: Specific Renal Alert Criteria and Actions

**Table 16-1 Specific Renal Alert Criteria and Actions**

Criteria	Action required
Serum creatinine (sCr) increase 25 – 49% compared to baseline	Consider causes and possible interventions Follow up within 2-5 days
Serum creatinine increase > 50%	Consider causes and possible interventions Repeat assessment within 24-48h if possible Consider drug interruption or discontinuation unless other causes are diagnosed and corrected Consider hospitalization and specialized treatment
Protein-creatinine or albumin-creatinine ratio increase $\geq$ 2-fold or new onset dipstick proteinuria $\geq$ 1+ or Albumin-creatinine ratio (ACR) $\geq$ 30 mg/g or $\geq$ 3 mg/mmol; or Protein-creatinine ratio (PCR) $\geq$ 150 mg/g or $>15$ mg/mmol	Consider causes and possible interventions Assess serum albumin & serum protein Repeat assessment to confirm Consider drug interruption or discontinuation unless other causes are diagnosed and corrected
New onset glucosuria on urine dipstick (unless related to concomitant treatment, diabetes)	Assess & document: Blood glucose (fasting) Serum creatinine Urine albumin-creatinine ratio
New hematuria on dipstick	Assess & document: Urine sediment microscopy Assess sCr and urine albumin-creatinine ratio Exclude infection, trauma, bleeding from the distal urinary tract/bladder, menstruation Consider bleeding disorder

Additional specialized assessments are available to assess renal function or renal pathology.  
(Note: In exceptional cases when a nephrologist considers a renal biopsy, it is strongly recommended to make specimen slides available for evaluation by Novartis to potentially identify project-wide patterns of nephrotoxicity.)

Whenever a renal event is identified, a detailed subject history and examination are indicated to identify, document and potentially eliminate risk factors that may have initiated or contributed to the event:

- Blood pressure assessment (after 5 min rest, with an appropriate cuff size)
- Signs and symptoms such as fever, headache, shortness of breath, back or abdominal pain, dysuria, hematuria, dependent or periorbital edema
- Changes in blood pressure, body weight, fluid intake, voiding pattern, or urine output
- Concomitant events or procedures such as trauma, surgical procedures, cardiac or hepatic failure, contrast media or other known nephrotoxin administration, or other potential causes of renal dysfunction, e.g., dehydration, hemorrhage, tumor lysis

